9.7.1.8.3 LABORATORY VALUES

Laboratory results will be summarized using International System of Units, as appropriate. For all quantitative parameters listed in [Section 9.5.1.5.3](#), the actual value and the change from baseline to each postbaseline visit and to the end of treatment (defined as the last on-treatment value) will be summarized by visit and treatment group using descriptive statistics. Qualitative parameters listed in [Section 9.5.1.5.3](#) will be summarized using frequencies (number and percentage of subjects), and changes from baseline to each postbaseline visit and to end of treatment will be reported using shift tables. Percentages will be based on the number of subjects with both nonmissing baseline and relevant postbaseline results.

Laboratory test results will be assigned a low/normal/high (LNH) classification according to whether the value was below (L), within (N), or above (H) the laboratory parameter's reference range. Within-treatment comparisons for each laboratory parameter will be based on 3-by-3 tables (shift tables) that compare the baseline LNH classification to the LNH classification at each postbaseline visit and at the end of treatment. Similar shift tables will also compare the baseline LNH classification to the LNH classification for the highest and lowest value during the treatment period.

[Appendix 1](#) (Sponsor's Grading for Laboratory Values) presents the criteria that will be used to identify subjects with treatment-emergent markedly abnormal laboratory values (TEMAVs). Except for phosphate, a TEMAV is defined as a postbaseline value with an increase from baseline to a Grade of 2 or higher. For phosphate, a TEMAV was defined as a postbaseline value with an increase from baseline to a Grade of 3 or higher. When displaying the incidence of TEMAVs, each subject may be counted once in the laboratory parameter high and in the laboratory parameter low categories, as applicable.

Lymphocyte subsets measured (including but not limited to CD4 [T helper cells], CD8 [cytotoxic T cells], CD19 [B cells], CD16/CD56 [natural killer cells] and CD14 [macrophages] and regulatory T cells) will be summarized in the same manner as other laboratory parameters. Mean lymphocyte subsets and the mean change from baseline in lymphocyte subsets will also be displayed graphically over time by dose.

Serum IgG, IgM, and IgA will be measured and summarized in the same manner as other laboratory parameters.

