9.5.1.5.3 LABORATORY MEASUREMENTS

Clinical laboratory tests to be performed, including hematology, chemistry, urinalysis, and CSF are summarized in [Table 4](#). Subjects should be in a seated or supine position during blood collection. [Table 6](#) and [Table 7](#) show the visits and time points at which blood for clinical laboratory tests and urine for urinalysis will be collected in the study.

See [Section 9.3.3](#) for safety criteria for discontinuation from study drug related to absolute counts of CD4, CD8, and B lymphocytes, and for lymphocyte subset counts.

Table 4 Clinical Laboratory Tests

| Category | Parameters |
|-----------------------------|--|
| Hematology | Hematocrit, hemoglobin, platelets, red blood cell count, and white blood cell count with differential (bands, basophils, eosinophils, lymphocytes, monocytes, neutrophils). PT, PTT, and INR (Screening and Baseline only) (revised per Amendment 02) |
| Chemistry | |
| Electrolytes | Bicarbonate, calcium, chloride, phosphate, potassium, sodium |
| Liver function tests | Alanine aminotransferase, alkaline phosphatase, aspartate aminotransferase, gamma glutamyl transpeptidase, direct bilirubin, total bilirubin |
| Renal function tests | Blood urea/blood urea nitrogen, creatinine |
| Other | Albumin, cholesterol, globulin, glucose, lactate dehydrogenase, total protein, triglycerides, uric acid |
| Urinalysis | Bacteria, casts, crystals, epithelial cells, glucose, ketones, occult blood, pH, protein, red blood cells, specific gravity, white blood cells |
| Other | Lymphocyte T and B cell subset analyses (see Table 5). Regulatory T cells (revised per Amendment 04) PBMCs (revised per Amendment 02) Ig analyses (IgG, IgA, and IgM). Viral screen (HCVAb [Hepatitis C] and HbsAg [Hepatitis B]). Viral characterization (including HSV1, HSV2 and CMV, etc) Serum pregnancy test (females of child bearing potential only) Tuberculosis Interferon Gamma Release Assays Tests for thyroid function (thyroid stimulating hormone, free triiodothyronine and free thyroxine) and vitamin B12 Blood sample for storage for subsequent testing of immune status Cerebrospinal fluid sampling |

Whenever unscheduled lymphocyte subset tests are performed or whenever scheduled lymphocyte subsets are repeated, a CBC with differentials must also be repeated. (revised per Amendment 02)

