- a. A study drug discontinuation threshold will be set based on absolute counts of CD4 (T helper cells), CD8 (cytotoxic T cells), or CD19 (B cells). The discontinuation threshold will be set at below the level of the population-adjusted LLN (CD4=396 cells/ μ L; CD8=157 cells/ μ L; and CD19=74 cells/ μ L), at a level that represents a greater risk of opportunistic infection in the treated population. (revised per Amendment 02) For CD4 (T helper cells) the discontinuation threshold is 250 cells/ μ L. For CD8 (cytotoxic T cells) and CD19 (B cells) the discontinuation thresholds are 150 cells/ μ L and 50 cells/ μ L, respectively. Any subject who has CD4 (T helper cells), CD8 (cytotoxic T cells), or CD19 (B cells) absolute counts below the discontinuation threshold as confirmed by a repeat test conducted within 1 week of the initial test but who has no clinical signs or symptoms of infection, will have study drug temporarily suspended for at least 2 weeks but no more than 4 weeks. During this period of study drug suspension, lymphocyte subset counts and complete blood count (CBC) with differentials will continue to be tested weekly until CD4 (T helper cells), CD8 (cytotoxic T cells), and CD19 (B cells) have all returned to greater than the population-adjusted LLN after which time study drug can be resumed. Testing of lymphocyte subset counts and CBC with differentials is required weekly for 4 weeks following resumption of study drug administration. Temporary suspension and rechallenge with study drug is only permitted once for any given subject. If the lymphocytes and CD counts do not return to greater than the population-adjusted LLN within 4 weeks from the start of temporary suspension the subject will need to be permanently discontinued from study drug. (revised per Amendment 04)
- b. Subjects with CD4 (T helper cells), CD8 (cytotoxic T cells), or CD19 (B cells) absolute counts between the population-adjusted LLN and the discontinuation threshold will have lymphocyte subset counts performed on a weekly basis. (revised per Amendments 02 and 04) During the early stages of the treatment period, where visits are conducted weekly (ie, Visits 4, 5, 6, and 7), lymphocyte subsets are already scheduled to be

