measured on a weekly basis and so additional visits or blood draws are not required. (revised per Amendment 02) For these subjects, the decision as to whether the subject remains on study drug or is to be discontinued from study drug will be based upon clinical judgment and will take into account any clinical presentation in addition to the lymphocyte subset counts. These subjects may continue with treatment if there is no clinical evidence of infection. They will be discontinued from study drug if they have infections of a moderate to severe intensity (eg, subjects whose infections are not localized, or are systemically unwell, or who require systemic anti-infective drug treatment).

Table 1 Study Drug Actions for Lymphocyte Subset Absolute Counts

| Lymphocyte subset absolute counts | Action | Decision to continue, discontinue, or temporarily suspend study drug |
|---|--|--|
| CD4 (T helper cells), CD8 (cytotoxic T cells), or CD19 (B cells) absolute counts below discontinuation threshold and no clinical signs or symptoms of infection | Retest within 1 week along with CBC with differentials | If retest performed within 1 week confirms lymphocyte subset counts below the discontinuation threshold, temporarily suspend study drug for between 2 and 4 weeks. Continue weekly testing of lymphocyte subsets and CBC with differentials. Rechallenge with study drug allowed when CD4 (T helper cells), CD8 (cytotoxic T cells), and CD19 (B cells) absolute counts all greater than population-adjusted LLN. Temporary suspension and rechallenge permitted only once for each subject. |
| CD4 (T helper cells), CD8 (cytotoxic T cells), or CD19 (B cells) absolute counts between population-adjusted LLN and discontinuation threshold | Lymphocyte subset counts (and CBC with differentials) to be performed weekly until lymphocyte subset counts return to \geq population-adjusted LLN | Decision will be based upon lymphocyte subset counts and clinical judgment |

LLN = lower limit of normal, CBC = complete blood count.

(Table revised per Amendments 02 and 04)

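### Low CD counts trigger extra weekly blood tests, and the any-value and extreme-value laboratory tables ignore the number of tests, so CBC abnormality rates can be modestly inflated in an arm with lower CD counts

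*Protocol*

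**What the plan says.** Protocol Section 9.3.3, item b, covers subjects with CD4, CD8 or CD19 between the population-adjusted LLN (396, 157 and 74 cells/µL) and the discontinuation threshold (250, 150 and 50 cells/µL). Such subjects "will have lymphocyte subset counts performed on a weekly basis". Table 1 adds the CBC and the stopping point: "Lymphocyte subset counts (and CBC with differentials) to be performed weekly until lymphocyte subset counts return to" the population-adjusted LLN or above. No maximum number of weeks or tests is given for this branch.

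The branch below the threshold is bounded. A subject with a confirmed low count and no infection "will have study drug temporarily suspended for at least 2 weeks but no more than 4 weeks". After that comes either permanent discontinuation or four weekly tests following resumption.

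Section 9.5.1.5.3 ties the CBC to every extra subset test: "Whenever unscheduled lymphocyte subset tests are performed or whenever scheduled lymphocyte subsets are repeated, a CBC with differentials must also be repeated".

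Section 9.7.1.8.3 sets the summaries. Except for phosphate, "a TEMAV is defined as a postbaseline value with an increase from baseline to a Grade of 2 or higher". A second set of tables takes extremes: "Similar shift tables will also compare the baseline LNH classification to the LNH classification for the highest and lowest value during the treatment period". Lymphocyte subsets are to be summarized like other laboratory parameters. Neither rule mentions scheduled visits or the number of draws, although other summaries in the same section are by visit. Section 9.7.1.1.1 places laboratory parameters in the primary endpoint.

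**The concern.** A table that counts a subject once if any value is abnormal, or that uses the subject's most extreme value, depends on how often the subject was tested. Here the testing frequency is set after randomization by CD counts, and Section 7.1 reports that the drug lowered CD counts in an earlier study. If one arm has lower counts, its subjects have more CBCs. Each extra CBC is another chance for neutrophils, platelets, leukocytes, hemoglobin or total lymphocytes to cross a limit, even where the drug does not affect that item.

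The trial is meant to guide dose selection for Phase 3 with about 15 subjects per arm. A reader of the TEMAV table who cannot see how many tests each arm had cannot tell a hematology signal from extra sampling.

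**Working it through.** The plan states no figure for this point, so there is none to reproduce. The check counts draws and then asks how far extra draws can move an arm.

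**Scheduled draws.** Table 7 has CBC and subset draws at weeks 1, 2, 3, 4, 6, 8, 10, 12, 16, 20, 26, 39, 52, 65 and 78. That is 15 on treatment (Visits 4 to 18), 4 of them after week 26. With 4 follow-up visits the total is 19; Table 8 lists 18. The difference of one does not matter here.

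**Extra draws for one subject.** A subject triggered at week 12 who never recovers has 78 − 12 = 66 weekly draws instead of 7 scheduled, so 59 extra. Triggered at week 4, 26 or 52, the extra is 63, 48 or 24. These are ceilings for one subject.

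**Effect on one subject.** Assume a constant chance p per draw of a Grade 2 or higher value, independent between draws. Then P(at least one) = 1 − (1 − p)^n.

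| p (assumed) | n = 15 | n = 27 | n = 41 | n = 15 + 59 = 74 |
|---|---|---|---|---|
| 0.5% | 7.2% | 12.7% | 18.6% | 31.0% |
| 1% | 14.0% | 23.8% | 33.8% | 52.5% |

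**Effect on an arm.** Most subjects never trigger, or recover, so the arm average matters. Section 9.4.4 gives a CD4 change at 100 mg of −3.1% against +8.7% on placebo, a relative gap of 1 − 0.969/1.087 = 11%. At 200 mg the fall was 22.9%. A simulation with all three CD triggers gave about 1 to 1.5 extra draws per subject for an 11% fall and 2 to 3.5 for a 22.9% fall.

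The formula is concave in n, so under independence spreading the extra draws evenly over all subjects gives the largest arm-level excess. Ceilings, using the upper ends:

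| p (assumed) | 15 draws | 16.5 draws (11% fall) | Excess | 18.5 draws (22.9% fall) | Excess |
|---|---|---|---|---|---|
| 0.5% | 7.2% | 7.9% | 0.7 points | 8.9% | 1.6 points |
| 1% | 14.0% | 15.3% | 1.3 points | 17.0% | 3.0 points |
| 2% | 26.1% | 28.3% | 2.2 points | 31.2% | 5.0 points |

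Repeated values within a subject are correlated and extra draws cluster in few subjects; both pull the excess below these figures.

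**Simulation with correlation, CD4 trigger only.** CD4 median 805 and 10th percentile 361 come from Table 12 (this study's column), with entry at 396 or above. Assumed: within-subject log-SD 0.15 or 0.25, and a CBC item with no drug effect and intraclass correlation 0.6.

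| CD4 fall | Mean draws | Scheduled only | All values |
|---|---|---|---|
| 0% | 15.6; 15.9 | 4.60%; 4.41% | 4.69%; 4.59% |
| 10% | 16.4; 16.7 | 4.57%; 4.59% | 4.82%; 4.83% |
| 22.9% | 19.0; 18.5 | 4.79%; 4.77% | 5.35%; 5.33% |

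(First figure log-SD 0.15, second 0.25.) Taking all values minus scheduled only, to remove simulation noise, the 22.9% fall adds (5.35 − 4.79) − (4.69 − 4.60) = 0.47 and (5.33 − 4.77) − (4.59 − 4.41) = 0.38 points. Among subjects who triggered at that fall, the rate is 6.0–6.8% on all values against 4.6–4.9% on scheduled visits.

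**What is not affected.** In the simulation the share of subjects ever low on CD4 was identical with and without repeats: a subject enters weekly testing only after being counted low. Appendix 1 grades no CD subset, so subsets have no TEMAVs.

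**The case against.** The strongest reply is that the protocol does not say unscheduled values enter these tables. Which records feed a laboratory table is often settled in the SAP, which is not shown. That limits the point but does not remove it. As written, the TEMAV rule takes any postbaseline value and the extreme tables take the highest and lowest value on treatment, without restriction, and that rule carries the bias.

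Second, the size. Section 9.4.4 says exposure at 50 mg with food is below that of the earlier 100 mg regimen, so a 22.9% fall lies beyond what this trial should produce. Subjects confirmed below the LLN at screening or baseline are excluded, visits are weekly up to week 4 anyway, and testing stops on recovery. All of this stands and is why the effect is called modest.

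Third, the by-visit summaries and by-visit shift tables in the same section are much less exposed, the shift tables are described as within-treatment, and safety is descriptive. That is also true. TEMAV incidence by treatment group will still be read across arms.

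Fourth, worst-value tables using every result are a sensible cautious choice when immune safety is the primary objective. This also stands, and the fix keeps them.

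A reader might infer that the amendments, which lowered the LLNs and dropped the trigger based on a fall of more than 33%, add to the bias between arms. They do not: they applied alike to all concurrently randomized arms.

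**Conclusion.** The point holds in a limited form. Testing frequency depends on a post-randomization count that the drug may lower, and the any-value and extreme-value summaries ignore it. TEMAVs for total lymphocytes, leukocytes, neutrophils, platelets and hemoglobin, and the highest/lowest shift tables for CBC items and non-triggering subsets, can be modestly inflated in an arm with lower CD counts. Part of any excess, notably in total lymphocytes, could be a true drug effect.

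The expected arm-level excess is roughly 0 to 3 percentage points. This rests on assumed per-draw abnormality rates, within-subject variation and size of CD fall, none of which the protocol gives. The 5-point ceiling above needs the 200 mg CD fall, a 2% rate per draw, independence and evenly spread extra draws together. One subject in an arm of 15 is 1/15 = 6.7 points, so the expected artefact is less than one subject.

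A reader might go further and conclude that an arm with falling counts must show more abnormalities, or that a false dose trend will appear. The documents do not support that. The low shift of the triggering subset is unaffected, the earlier data cited point to at most a small CD effect at the top dose, and 78 weeks of weekly testing describes no arm.

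**What to change.** In Section 9.7.1.8.3:

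- Keep the all-values TEMAV and highest/lowest tables.
- Beside them, add versions restricted to scheduled visits (on treatment, Visits 4 to 18) for reading between arms: TEMAVs for CBC items, and highest/lowest shifts for CBC items and lymphocyte subsets.
- Report the number of CBC and subset tests per subject by arm.

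The monitoring rules in Section 9.3.3 stay as they are. The cost is analysis-plan wording and a few more tables from data already collected. The drawback is that a scheduled-only table can miss a nadir between visits, especially once visits are 13 weeks apart; the retained all-values tables cover that.

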9.7.1.8.4 VITAL SIGNS

Descriptive statistics for vital signs parameters (ie, systolic and diastolic BP, pulse, respiratory rate, temperature, weight), and changes from baseline will be presented by visit and treatment group.

9.7.1.8.5 ELECTROCARDIOGRAMS

Descriptive statistics for ECG parameters and changes from baseline will be presented by visit and treatment group. Shift tables will present changes from baseline in ECG interpretation (categorized as normal; abnormal, not clinically significant; and abnormal, clinically significant) to the end of treatment.

In addition, the number (percentage) of subjects with at least 1 postbaseline abnormal ECG result in QTcF during the treatment period will be summarized. Clinically abnormal ECG results in QTcF will be categorized as follows:

Absolute QTc interval prolongation:

- QTc interval >450 msec
- QTc interval >480 msec
- QTc interval >500 msec

Change from baseline in QTc interval:

- QTc interval increases from baseline >30 msec
- QTc interval increases from baseline >60 msec

9.7.1.8.6 OTHER SAFETY ANALYSES

Cognitive decline will be assessed as a safety assessment, in addition to efficacy assessments. Cognitive assessments will include CBB ([Section 9.7.1.6](#)). (revised per Amendment 05)

9.7.2 Determination of Sample Size

A total of 15 subjects per dose group is deemed sufficient to derive adequate safety and PK/PD data to aid in the selection of appropriate doses and the design of the Phase 3 studies that may be planned subsequently. (revised per Amendment 05)

9.7.3 Interim Analysis

In order to make decisions about the remainder of the study as well as the full E2609 clinical development program, the sponsor will unblind safety, PK, and PD data on an ongoing basis and perform interim analyses of these data. Investigators, other clinical site staff, subjects, caregivers/informants, and study team will remain blinded to study treatment. (revised per Amendments 03 and 05)

An interim safety analysis will also be conducted when all subjects have completed 12 weeks of treatment (or discontinue study drug early). (revised per Amendments 01, 03, 04, and 05)

9.7.4 Other Statistical/Analytical Issues

Stratification (revised per Amendment 01)

Within the 2 clinical cohorts (MCI/Prodromal and mild to moderate AD), subjects will be stratified at randomization by *ApoE4* status (positive or negative) and prior treatment with AChEIs or memantine or both (yes or no). (revised per Amendment 01)

9.7.5 Procedure for Revising the Statistical Analysis Plan

If the statistical analysis plan needs to be revised after the study starts, the sponsor will determine how the revision impacts the study and how the revision should be implemented. The details of the revision will be documented and described in the clinical study report.

11 PROCEDURES AND INSTRUCTIONS (ADMINISTRATIVE PROCEDURES)

11.1 Changes to the Protocol

Any change to the protocol requires a written protocol amendment or administrative change that must be approved by the sponsor before implementation. Amendments specifically affecting the safety of subjects, the scope of the investigation, or the scientific quality of the study require submission to health or regulatory authorities as well as additional approval by the applicable IRBs/IECs. These requirements should in no way prevent any immediate action from being taken by the investigator, or by the sponsor, in the interest of preserving the safety of all subjects included in the study. If the investigator determines that an immediate change to or deviation from the protocol is necessary for safety reasons to eliminate an immediate hazard to the subjects, the sponsor's medical monitor and the IRB/IEC for the site must be notified immediately. The sponsor must notify the health or regulatory authority as required per local regulations.

Protocol amendments that affect only administrative aspects of the study may not require submission to health or regulatory authority or the IRB/IEC, but the health or regulatory authority and IRB/IEC (or if regionally required the head of the medical institution) should be kept informed of such changes as required by local regulations. In these cases, the sponsor may be required to send a letter to the IRB/IEC and the Competent Authorities (or, if regionally required, the head of the medical institution) detailing such changes.

11.2 Adherence to the Protocol

The investigator will conduct the study in strict accordance with the protocol (refer to ICH E6, Section 4.5).

11.3 Monitoring Procedures

The sponsor's or CRO's CRA will maintain contact with the investigator and designated staff by telephone, letter, or email between study visits. Monitoring visits to each site, and potential remote source document verification, will be conducted by the assigned CRA as described in the monitoring plan. The investigator (or if regionally required, the head of the medical institution) will allow the CRA to inspect the clinical, laboratory, and pharmacy facilities to assure compliance with GCP and local regulatory requirements. The eCRFs and subject's corresponding original medical records (source documents) are to be fully available for review by the sponsor's representatives at regular intervals. These reviews verify adherence to study protocol and data accuracy in accordance with local regulations. All records at the site are subject to inspection by the local auditing agency and to IRB/IEC review.

In accordance with ICH E6, Section 1.52, source documents include, but are not limited to, the following:

- Clinic, office, or hospital charts
- Copies or transcribed health care provider notes that have been certified for accuracy after production
- Recorded data from automated instruments such as IxRS, x-rays, and other imaging reports (eg, sonograms, computed tomography scans, MRIs, radioactive images, ECGs, rhythm strips, electroencephalography, polysomnographs, pulmonary function tests) regardless of how these images are stored, including microfiche and photographic negatives
- Pain, quality of life, or medical history questionnaires completed by subjects
- Records of telephone contacts
- Diaries or evaluation checklists
- Drug distribution and accountability logs maintained in pharmacies or by research personnel
- Laboratory results and other laboratory test outputs (eg, urine pregnancy test result documentation and urine dip-sticks)
- Correspondence regarding a study subject's treatment between physicians or memoranda sent to the IRBs/IECs
- CRF components (eg, questionnaires) that are completed directly by subjects and serve as their own source

